### 2.8.2.1 Other safety data

#### ECGs

ECG data will be analyzed based on central laboratory reported results. The summaries will include all ECG assessments performed in the on-treatment period. All ECG assessments will be listed, and those collected prior to first dose of study drug or later than 30 days after study drug discontinuation will be flagged in the listing.

#### Selecting Primary QT Correction for Heart Rate

The analysis of QT data is complicated by the fact that the QT interval is highly correlated with heart rate. Because of this correlation, formulas are routinely used to obtain a corrected value, denoted QTc, which is independent of heart rate. This QTc interval is intended to represent the QT interval at a standardized heart rate. Several correction formulas have been proposed in the literature. For this analysis we will use some of those methods of correction, as described below. The QT interval corrected for heart rate by the Bazett's formula, QTcB, is defined as

$$QTcB = \frac{QT}{\sqrt{RR}},$$

the QT interval corrected for heart rate by the Fridericia's formula, QTcF, is defined as

$$QTcF = \frac{QT}{\sqrt[3]{RR}}$$

where RR represents the RR interval of the ECG, in seconds.

Although Bazett's correction is the historical standard, it does not perform well when heart rate fluctuates. Fridericia's formula may perform better under these conditions. An alternate correction to achieve the goal of getting uncorrelated QTc and RR is based on linear or log-linear regression methods which yield, theoretically, uncorrelated QTc and RR.

Linear regression method:

- Fit a model  $QT = a + b * RR$  to baseline data
- Use the estimated slope,  $\hat{b}$ , to correct QT
- Corrected QT for heart rate will be computed as follows:

$$QTcP = QT + \hat{b} * (1 - RR)$$

Data will be summarized using QTcF and QTcB. However, if these are not appropriate for the data set due to an observed large correlation between corrected QT and HR using the baseline assessments, the results will also be summarized using QTcP.

#### ECG Summaries

The following analyses will be performed for each applicable ECG parameters (RR, PR, QRS, QT, ventricular rate – denoted as HR in what follows, and QTc) as noted.

- Pearson correlation between QT and HR, QTc (QTcB, QTcF and, if applicable, QTcP) and HR using individual (non-averaged) baseline assessments and separately using on-treatment assessments
- For each of the ECG parameters (HR, and QT, QTc, QRS, PR intervals), descriptive statistics at baseline, at each post-baseline time point and changes from baseline at each post-baseline time point
- For each of the QTc and QT intervals, shift tables based on notable parameter categories ( $\leq 450$ ,  $>450 - \leq 480$ ,  $>480 - \leq 500$ ,  $>500$  ms) at baseline and the worst post-baseline value observed
- Frequency counts and percentages of patients having notable ECG values according to the following categories:
  - QT parameter (QT, QTc) increase from baseline  $>30$  ms,  $>60$  ms
  - Newly occurring post-baseline QT parameter  $> 450$  ms,  $> 480$  ms,  $> 500$  ms
  - HR increase from baseline  $> 25\%$  and value  $> 100$  bpm
  - HR decrease from baseline  $> 25\%$  and value  $< 50$  bpm
  - PR increase from baseline  $> 25\%$  and value  $> 200$  ms
  - Newly occurring post-baseline PR  $> 200$  ms and  $\leq 220$  ms,  $> 220$  ms
  - QRS increase from baseline  $> 25\%$  and value  $> 110$  ms
  - Newly occurring post-baseline QRS  $> 110$  ms and  $\leq 120$ ms,  $> 120$  ms

The denominator to calculate percentages for each category is the number of patients at risk for a specific category. For new abnormality post baseline values, this is the number of patients with both baseline and post baseline, and baseline not meeting the criteria. For abnormal change from baseline, this is the number of patients with both baseline and post baseline evaluations. A newly occurring post-baseline ECG notable value is defined as a post-baseline value that meets the criterion post-baseline but did not meet the criterion at baseline

- Frequency counts and percentages of patients with newly occurring post-baseline qualitative ECG abnormalities (morphology) will be summarized. The denominator to calculate percentages for any newly occurring ECG abnormality, each abnormality type and each individual finding is the number of patients with both a baseline and a post-baseline evaluation, and baseline being normal, i.e. those patients who are at risk of developing this abnormality. A newly occurring post-baseline qualitative ECG abnormality is defined as a post-baseline abnormal finding which was not present at baseline

Patients with notable ECG interval values and newly occurring qualitative ECG abnormalities will be listed by patient, time point and the corresponding notable values and abnormality findings will be included in the listings.

Unscheduled ECG measurements will not be used in computing the descriptive statistics for change from baseline at each post-baseline time point. However, they will be used in the analysis of notable ECG changes and the shift table analysis of notable QT parameters.

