### 4.7.1 Multiple assessments within post-baseline visits

For all analyses regarding abnormal assessments or analyses based on worst or best post-baseline value (laboratory, ECGs, vital signs, WHO performance status), all post-baseline values will be included (scheduled, unscheduled, repeat). All unscheduled and repeat measurements will be included in listings.

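### The SAP's newly occurring rule counts PR and QRS intervals that improve into a closed band as new ECG abnormalities

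*SAP*

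**What the plan says.** SAP 2.8.2.1, under ECG Summaries, lists the interval categories. Those headed "Newly occurring post-baseline QT parameter" are open-ended: above 450, 480 and 500 ms. Those headed "Newly occurring post-baseline PR" are a band above 200 up to 220 ms and an open category above 220 ms. Those headed "Newly occurring post-baseline QRS" are a band above 110 up to 120 ms and an open category above 120 ms.

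A value is newly occurring if it is "a post-baseline value that meets the criterion post-baseline but did not meet the criterion at baseline". For the denominator, "this is the number of patients with both baseline and post baseline, and baseline not meeting the criteria".

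For qualitative (morphology) findings, one denominator serves any abnormality, each type and each individual finding: "the number of patients with both a baseline and a post-baseline evaluation, and baseline being normal, i.e. those patients who are at risk". The sentence goes on to tie that risk to the particular abnormality. A new finding "is defined as a post-baseline abnormal finding which was not present at baseline".

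SAP 4.7.1 makes every scheduled, unscheduled and repeat post-baseline value eligible for analyses of abnormal assessments. The ECG section names the worst post-baseline value only for the QT and QTc shift tables.

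**The concern.** Newly occurring should mean that the patient got worse. The stated rule has no direction in it. It asks only whether the criterion holds after baseline and did not hold before. With a closed band there are two ways not to meet the criterion at baseline, below the band or above it, and the rule treats them alike.

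PR and QRS have no shift table in the SAP, so these rows are their only summary by absolute level that does not also require a rise of more than 25%. SAP Section 2 is to be carried into the clinical study report as the statistical methods, so the rule would become the reported method.

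The morphology wording raises a smaller, related question. If a normal baseline means a wholly normal ECG, a patient with one abnormality at baseline and a different one later meets the numerator definition but is outside the denominator.

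**Working it through.** The plan states no ECG count or percentage, so there is no figure to reproduce.

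**1. Which categories can count an improvement.** Let b be the baseline value, p a post-baseline value and C the criterion. The SAP counts a patient as at risk if C(b) is false, and as new if C(b) is false and C(p) is true. An improvement is p < b.

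- One-sided category, x > L: C(b) false gives b ≤ L, and C(p) true gives p > L, so p > b. An improvement can never be counted.
- Closed band, L < x ≤ U: C(b) false gives b ≤ L or b > U. If b > U and p is in the band, then p ≤ U < b. Every such count is an improvement.

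A search of all integer pairs from 80 to 599 ms confirmed this: improvements are counted in exactly two of the seven categories, the PR band and the QRS band.

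| Baseline → later value (ms) | At risk in band row | New in band row |
|---|---|---|
| PR 190 → 210 | yes | yes (correct) |
| PR 230 → 210 | yes | yes (an improvement) |
| QRS 100 → 116 | yes | yes (correct) |
| QRS 126 → 116 | yes | yes (an improvement) |

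If any reading may qualify, PR 190 → 210 → 230 also counts in both PR rows.

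**2. Illustrative size for the PR band.** N = 156 is the number enrolled (Protocol, Amendment 6 rationale). The rest is assumed: 5% of baselines already in the band (8 patients); 2% to 10% above 220 ms (3 to 16); 5% of those at or below 200 ms truly entering the band (7); 25% to 50% of those above 220 ms falling into it (1 to 8).

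- As written: (true new + improved) / (baseline ≤ 200 + baseline > 220).
- Corrected: true new / baseline ≤ 200.
- Low case: baseline ≤ 200 is 156 − 3 − 8 = 145. As written (7 + 1)/(145 + 3) = 8/148 = 5.4%; corrected 7/145 = 4.8%.
- High case: baseline ≤ 200 is 156 − 16 − 8 = 132. As written (7 + 8)/(132 + 16) = 15/148 = 10.1%; corrected 7/132 = 5.3%.

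**3. Morphology, literal reading, any new finding.** Assume a 20% risk of a new finding whatever the baseline.

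- 30% abnormal at baseline: 109 normal, 47 abnormal; new findings 22 + 9 = 31. Literal 31/109 = 28.4%. Matched: 22/109 = 20.2% in normals, or 31/156 = 19.9% in all.
- 70% abnormal at baseline: 47 normal, 109 abnormal; new findings 9 + 22 = 31. Literal 31/47 = 66.0%. Matched: 9/47 = 19.1%, or 31/156 = 19.9%.
- At 70% abnormal and a 40% risk, the literal figure is 63/47 = 134%. A percentage above 100 shows that the numerator is not contained in the denominator.

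**The case against.** Three objections carry weight.

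First, the SAP does not say whether a patient is placed in a PR or QRS row on any reading or on the worst one, and adjoining rows (above 200 up to 220, then above 220) are compatible with the worst. This matters for a stronger claim that a reader might infer: that measurement noise alone would push most patients just above 220 ms into the band. With an assumed within-patient SD of 6 ms and the eight post-baseline ECG time points through Cycle 6 Day 1 in Protocol Table 7-5, 1 − (1 − Φ((220 − b)/6))^8 gives 75% at a baseline of 226 ms. It falls to 32% at 230, 5% at 235 and 0.3% at 240. The result depends on an SD that is not in the documents, on baselines close to the limit, and on any-reading classification. On the worst-value reading, a patient who fluctuates around 226 ms would almost always stay above 220 and not be counted. That claim is not supported. The defect survives either reading, because a sustained fall from 230 to 210 ms is still counted.

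Second, a reader might infer that every morphology percentage is wrong. The sentence defining the denominator refers to risk of the particular abnormality, so a normal baseline can be read as normal for that finding. Numerator and denominator then agree for individual findings. What remains is a mismatch on the literal reading, and an unclear denominator for the type and any-abnormality rows.

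Third, there are other safeguards. The SAP has PR and QRS rows that require a rise of more than 25%, change-from-baseline statistics, and listings by patient and time point. An entry into the band from above can be seen there. This limits the harm but does not correct the tabulated percentage.

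**Conclusion.** The main point holds for two categories only, PR above 200 up to 220 ms and QRS above 110 up to 120 ms. As written, the rule counts improvement into the band as a new abnormality and treats patients already above the band as at risk of it. This follows from the text and needs no assumption. The size does: neither the share of baselines above 220 ms (PR) or 120 ms (QRS) nor the share with an abnormal baseline ECG is given, so the percentages above are illustrations. If no patient starts above a band, the effect on that row is nil.

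The morphology point is secondary: wording that two programmers could implement differently.

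Because QTc prolongation and bradycardia are adverse events of special interest, a reader might infer that those results are distorted. They are not. The QT categories are one-sided, the heart-rate categories require a directional change, the events of special interest are identified from preferred terms, and neither PR nor QRS prolongation is on that list. Efficacy results and sample size are untouched; the study tests no hypothesis.

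**What to change.** In SAP 2.8.2.1:

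- For the PR and QRS bands, require a baseline at or below the band's lower limit (PR ≤ 200 ms, QRS ≤ 110 ms) in both numerator and denominator, and classify each patient on the worst post-baseline value. Each patient then appears in at most one PR row and one QRS row.
- For each morphology finding or type, use as denominator the patients with baseline and post-baseline ECGs in whom that finding or type was absent at baseline.
- For the row of any new abnormality, restrict the numerator to the patients in its denominator. If that denominator stays at patients with a normal baseline ECG, new findings in the others drop out of this row but still appear in the rows by finding.

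The cost is a few lines of SAP text and a small program change. No new data are needed.

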## Vital signs

Vital sign assessments will be performed in order to characterize basic body function. The parameters collected are weight (kg), body temperature (°C), pulse rate (beats per minute), and sitting systolic and diastolic blood pressure (mmHg).

Clinically notable elevated values are defined as:

- Systolic BP:  $\geq 160$  mmHg and an increase  $\geq 20$  mmHg from baseline
- Diastolic BP:  $\geq 100$  mmHg and an increase  $\geq 15$  mmHg from baseline.
- Body temperature:  $\geq 39.1^{\circ}\text{C}$
- Weight: increase from baseline of  $\geq 10\%$
- Pulse rate:  $\geq 120$  bpm with increase from baseline of  $\geq 15$  bpm

Clinically notable below normal values are defined as:

- Systolic BP:  $\leq 90$  mmHg and a decrease  $\geq 20$  mmHg from baseline
- Diastolic BP:  $\leq 50$  mmHg and a decrease  $\geq 15$  mmHg from baseline
- Body temperature:  $\leq 35^{\circ}\text{C}$
- Weight: decrease from baseline of  $\geq 10\%$
- Pulse rate:  $\leq 50$  bpm with decrease from baseline of  $\geq 15$  bpm

Vital signs shift table based on values classified as notable low, normal, notable high or notable (high and low) at baseline and worst post-baseline will be produced for pulse rate, diastolic BP and systolic BP.

Descriptive statistics will be tabulated by study arm for baseline and changes from baseline to worst post-baseline value for each vital sign measure.

Patients with clinically notable vital sign abnormalities will be listed by study arm. All vital sign assessments will be listed by study arm, patient and vital sign parameter.

In the listings, clinically notable values will also be flagged.

### WHO performance status

[figure not shown]
The WHO performance assessment allows patients to be classified as to their functional impairment, the definition of scores in relation to their performance status is provided in [Table 2-3](#), ranging from 0 (most active) to 5 (dead):

[figure not shown]
**Table 2-3 WHO performance scale**

Score	Description
0	Fully active, able to carry on all pre-disease performance without restriction
1	Restricted in physically strenuous activity but ambulatory and able to carry out work of a light or sedentary nature, e.g., light house work, office work
2	Ambulatory and capable of all self-care but unable to carry out any work activities. Up and about more than 50% of waking hours
3	Capable of only limited self-care, confined to bed or chair more than 50% of waking hours
4	Completely disabled. Cannot carry on any self-care. Totally confined to bed or chair
5	Dead

For all analyses regarding WHO, non-missing post-baseline questionnaire assessments within 30 days of last dose of study treatment, and before the start of any further anti-neoplastic therapies will be used.

Shift tables of WHO performance status at baseline to worst post-baseline WHO status by score will be provided; shift tables of WHO performance status at baseline to best post-baseline WHO status by score will also be provided. WHO performance status at each time point will be listed.

[figure not shown]

[figure not shown]

[Redacted text block]

**2.8.6 Patient-report outcomes**

Not applicable.

## 2.9 Sample size calculation

The study will enroll approximately 160 patients, with approximately 40 patients each in Arms 1 and 2 and ~30 patients each in Arms 3 and 4 and at least 20 patients in Arm 5 (See [Table 2-4](#)). It is assumed that 5% of the patients diagnosed with brain metastases have leptomeningeal carcinomatosis. Additional patients in Arm 4 may be enrolled in order to achieve approximately 60 patients in Arms 3 and 4 together (i.e. ALKi naïve patients) if enrollment rate in Arm 3 is slow.

An observed ORR of 50% in 140 patients planned for Arms 1-4 will result in an exact binomial 95% CI with a lower bound greater than 40% which is clinically meaningful and exceeds the ORR expected with available therapies ([Shaw 2012](#)). [Table 2-4](#) provides the exact binomial 95% CI for various observed ORRs for the 140 patients and for each of the strata.

**Table 2-4 Exact binomial 95% confidence intervals for various observed ORRs**

Sample Size	Observed ORR	Number of Patients with Confirmed PR or CR	Exact 95% CI
N=140 (overall Arms 1-4)	50%	70	(41.44%, 58.56%)
	60%	84	(51.39%, 68.18%)
N=80 (Arms 1 and 2)	40%	32	(29.20%, 51.56%)
	50%	40	(38.60%, 61.40%)
	60%	48	(48.44%, 70.80%)
N=40 (each of Arms 1 or 2)	40%	16	(24.87%, 56.67%)
	50%	20	(33.80%, 66.20%)
N=30 (each of Arms 3 or 4)	60%	18	(40.60%, 77.34%)
	70%	21	(50.60%, 85.27%)

## 2.10 Power for analysis of key secondary variables

Estimation of the DCR is the key secondary objective of the study. An observed DCR of 65% in 140 patients in Arms 1-4 will result in an exact binomial 95% CI with a lower bound greater than 55%. [Table 2-5](#) provides the exact binomial 95% CI for various observed DCRs for the 140 patients and for each of the strata.

**Table 2-5 Exact binomial 95% confidence intervals for various observed DCRs**

Sample Size	Observed DCR	Number of Patients with SD, PR or CR	Exact 95% CI
N=140 (overall Arms 1-4)	65%	91	(56.49%, 72.86%)
	75%	105	(66.98%, 81.93%)
N=80 (Arms 1 and 2)	60%	48	(48.44%, 70.80%)
	70%	56	(58.72%, 79.74%)
N=40 (each of Arms 1 or 2)	60%	24	(43.33%, 75.14%)
	70%	28	(53.47%, 83.44%)
N=30 (each of Arms 3 or 4)	70%	21	(50.60%, 85.27%)
	80%	24	(61.43%, 92.29%)

An additional secondary objective of the study is estimation of the OIRR for patients with measurable brain metastases at baseline. As described in [Section 4.1.1 of the study protocol](#), the study targets enrolling approximately 70 patients with measurable brain metastases: ~50 patients with prior ALKi treatment (Arms 1 and 2) and ~20 patients with no prior ALKi treatment (Arms 3 and 4). An observed OIRR of 50% in 70 patients with measurable brain metastases will result in an exact binomial 95% CI with a lower bound greater than 35%. An observed OIRR of 60% in 50 patients with measurable brain metastases previously treated with ALKi (Arms 1 and 2) will result in an exact binomial 95% CI with a lower bound greater than 45%. An observed OIRR of 60% in 20 patients with measurable brain metastases not previously treated with ALKi (Arms 3 and 4) will result in an exact binomial 95% CI with a lower bound greater than 36% ([Table 2-6](#)). The reported OIRR with crizotinib is 18% (95% CI: 5 - 40) for patients with measurable brain metastases and prior radiation therapy to the brain, and 33% (95% CI: 13 - 59) for patients without prior radiation to the brain; recent whole brain radiation was allowed ([Crino et al 2013](#)).

**Table 2-6 Exact binomial 95% confidence intervals for various observed OIRRs**

	Observed OIRR	Number of Patients with Confirmed PR or CR in the brain	Exact 95% CI
N=70 (Overall)	45%	32	(33.74%, 58.06%)

Arms 1-4)	50%	35	(37.80%, 62.20%)
	55%	39	(43.34%, 67.59%)
	60%	42	(47.59%, 71.53%)
N=50 (prior ALKi treatment, Arms 1+2)	40%	20	(26.41 %, 54.82 %)
	45%	23	(31.81 %, 60.68 %)
	50%	25	(35.53%, 64.47%)
	55%	28	(41.25%, 70.01%)
	60%	30	(45.18%, 73.59%)
N=20 (no prior ALKi treatment, Arms 3+4)	50%	10	(27.20%, 72.80%)
	55%	11	(31.53%, 76.94%)
	60%	12	(36.05%, 80.88%)
	65%	13	(40.78%, 84.61%)

### 3 Changes to protocol specified analyses

Table 3-1 summarizes the changes to protocol-specified analyses and associated rationale for inclusion in Appendix 16.1.9 (Documentation of Statistical Methods) of the CSR.

**Table 3-1 Changes to protocol specified analysis or descriptions and rationale**

Protocol Section	Protocol Description	Change
Section 10.5.2	The distribution function of TTIR will be estimated using the Kaplan-Meier method. The median TTIR along with 95% CI will be presented. TTIR will be summarized by prior radiotherapy to the brain (yes, no), prior ALK inhibitor use (yes, no) and overall using the data from Arms 1 through 4. Similar for TTER and TTR.	TTIR will be summarized by frequency counts in time intervals and using descriptive statistics for patients with confirmed CR or PR. This analysis is removed. This update was made because median value is not estimable using KM method due to low response rate. Descriptive statistics suggested median

---

		values were consistent across study arms.
Section 10.5.2	A patient who has not progressed or died at the date of the analysis or when he/she receives any further anticancer therapy in the absence of disease progression will be censored at the time of the last adequate tumor evaluation before the earlier of the cut-off date or the anticancer therapy date.	A patient who has not progressed or died at the date of the analysis cut-off will be censored at the time of the last adequate tumor evaluation performed on or before the cut-off date. This update was made to align with the latest “Guidelines for response, duration of overall response, TTF, TTP, progression-free survival, and overall survival”.

---

